8.1.1.2. Planned Principal Secondary Efficacy Statistical Analyses

Principal Secondary Efficacy Statistical Analyses: Average Monthly IV Iron Dose
Endpoint(s)

 • Average monthly IV iron dose (mg)/subject from baseline to Week 52
Model Specification

 • Average monthly IV iron dose (mg)/subject from baseline to Week 52 will be determined by calculating the total IV iron dose per subject from Day 1 to the earliest of ((Week 52 visit date, first blood (RBC or whole blood) transfusion date, and treatment stop date + 1 day) which corresponds to the time while the subject was on randomized treatment and before receiving a blood transfusion. This total IV iron dose will be divided by (the number of days from Day 1 to the earliest of (Week 52 visit date, first blood transfusion date (RBC or whole blood), and treatment stop date +1) /30.4375 days). See Section 10.4 for the definition of on-treatment IV iron. • An ANCOVA model will be used to compare the difference in average monthly IV iron dose per subject between arms, adjusting for: 
 ○ Treatment ○ Baseline monthly IV iron dose (see Section 10.5.2) ○ Dialysis type (as randomized, see Section 0) ○ Dialysis start manner (whether dialysis start is planned or unplanned; as randomized, see Section 0).
Model Results Presentation

 • The number and percentage of subjects with baseline IV iron use, on-treatment EP IV iron use, and on-treatment IV iron use to Week 52 will be summarized by treatment. • Average monthly IV iron dose at baseline, while on treatment during the EP, and while on treatment to Week 52 will be summarized by treatment group using mean, standard deviation, minimum, P25, median, P75, and maximum. • The least square (LS) mean estimates and standard errors by treatment group, LS mean difference, two-sided 95% CI and one-sided superiority p-value for the difference in average monthly IV iron dose/subject to Week 52 between the daprodustat and darbepoetin alfa arms from the ANCOVA model will be presented. The number of subjects contributing to the analysis and the associated mean and standard deviation of the baseline and Week 52 values will also be displayed with the results of the ANCOVA model. • A listing of average monthly IV iron dose will be provided including treatment, site ID, unique subject ID, time period, and average monthly IV iron dose to Week 52.

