
 If the frequency of the record is not 'one time dose', then duration is calculated as follows: 
 If the concomitant medication record start date \geq Randomization date, the duration of the record is 0. If the concomitant medication record end date + gap factor < (Randomization date – 10 weeks), the duration of the record is 0. If the concomitant medication record end date + gap factor \geq (Randomization date – 10 weeks) or the record is ongoing, the duration of the record will be calculated as Stop Date – Start Date +1 day where: 
 Start date will be the latest of (concomitant medication record start date and the Randomization date – 10 weeks). Stop date will be the earliest of (concomitant medication record stop date + gap factor and the day before randomization). If the frequency of the record is 'one time dose', then: 
 If concomitant medication record start date < Randomization date – 10 weeks, or if Randomization date \leq concomitant medication record start date, then duration of the record is 0. If Randomization date – 10 weeks \leq concomitant medication record start date < Randomization date, then: 
 Frequency (for standardization formula) = 1 Duration = 7 days The total dose for each IV iron record will be: Standardized dose*duration/7 days A weighted mean will then be used to obtain the baseline monthly IV iron dose: 		

CONFIDENTIAL

201410

Iron Endpoints		

 ○ Mean baseline monthly IV iron dose = $[(\text{IV iron total dose}_{\text{Record 1}}) + \dots + (\text{IV iron total dose}_{\text{Record n}})] / [(\text{Randomization Date} - \text{Screening Week -2 Visit Date}) / 30.4375 \text{ days}]$. 		
Standardized IV Iron Dose (mg/month) from Randomization to Week 52		

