
 ● In order to calculate the average monthly IV iron dose from Randomization to Week 52, the dose of IV iron will be standardized to obtain a continuous single unit IV iron dose in terms of mg/month for the period from the Randomization date to the Week 52 visit date while the subject is on treatment and before their first RBC or whole blood transfusion. 
 ○ Note: Subjects who are randomized but never treated will not have a value for average monthly IV iron from Randomization to Week 52. ● IV iron therapy concomitant medication records that occur or are ongoing during the period from the subject's Randomization date – 10 weeks to the Week 52 visit date will be selected and ordered by start date and end date. ● The standardization will be carried out with the following formula: 
 ○ Standardized IV iron dose (mg/week) = IV iron drug dose (mg) * frequency 		
Note: Frequency and Gap Factors defined as follows:		
Frequency (from eCRF)	Frequency (for standardization formula)	Gap Factor
2 times per week	2	2.5 days
3 times per week	3	1.33 days
4 times per week	4	0.75 day
5 times per week	5	0.4 day
BID	14	0 days
Once daily	7	0 days
One time dose	1	n/a
Every 12 Hours	14	0 days
Every 2 weeks	0.5	13 days
Every 4 weeks	0.25	27 days
Once a month	0.23	29 days
Once a week	1	6 days
TID	21	0 days

 ● If the frequency of the record is not 'one time dose', then duration is calculated as follows: 
 ○ If the concomitant medication record start date > earliest of (treatment stop date +1 and Week 52 visit date), the duration of the record is 0. ○ If the concomitant medication record end date + gap factor < Randomization date, the duration of the record is 0. ○ If the concomitant medication record end date + gap factor \geq Randomization date or the record is ongoing, the duration of the record will be calculated as Stop Date – Start Date +1 day where: 
 ▪ Start date will be the latest of (concomitant medication record start date, randomization date, treatment start date). 		

CONFIDENTIAL

201410

Iron Endpoints		

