
 ▪ Stop date will be the earliest of (concomitant medication record stop date + gap factor, first transfusion date (RBC or whole blood), treatment stop date + 1, and the Week 52 visit date). • If the frequency of the record is 'one time dose', then: 
 ○ If concomitant medication record start date < treatment start date, or if earliest of (first transfusion date (RBC or whole blood), treatment stop date + 1 and Week 52 visit date) < concomitant medication record start date, then duration of the record is 0. ○ If latest of (Randomization date, treatment start date) ≤ concomitant medication record start date ≤ earliest of (first transfusion date (RBC or whole blood), treatment stop date + 1 and Week 52 visit date), then: 
 ▪ Frequency (for standardization formula) = 1 ▪ Duration = 7 days • The total dose for each IV iron record will be: Standardized dose*duration/7 days • A weighted mean will then be used to obtain the monthly IV iron dose from Randomization to Week 52: Mean monthly IV iron dose from Randomization to Week 52 while on treatment = $[(IV \text{ iron total dose}_{Record 1}) + \dots + (IV \text{ iron total dose}_{Record n})] / \{[\text{earliest of (treatment stop date + 1, Week 52 Visit Date)} - \text{treatment start date} + 1] / 30.4375 \text{ days}\}$. 		
Standardized Monthly IV Iron Dose (mg/month) from Week 28 to Week 52 (EP Average Monthly IV Iron Dose)		

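### Recurring-frequency IV iron records that end shortly before randomization have part of their dose counted as on-treatment iron in the principal secondary endpoint and lost from the baseline covariate

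*SAP*

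**What the plan says.** Three places in the SAP define which iron belongs where.

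- **8.1.1.2** says the endpoint "will be determined by calculating the total IV iron dose per subject from Day 1 to the earliest of" the Week 52 visit, the first transfusion, or treatment stop plus one day. It refers to Section 10.4 for what counts as on-treatment IV iron.
- **10.4.1.1**, which names the IV iron dose endpoints, treats a date on or before treatment start as pre-treatment and only later dates as on-treatment.
- **10.5.2.1** (footnote 1) defines the baseline covariate as all IV iron in the 10 weeks before randomization.

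The derivation in **10.6.3.2** works record by record: dose, times weekly frequency, times credited days, divided by 7.

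- *Selection for Randomization to Week 52:* "IV iron therapy concomitant medication records that occur or are ongoing during the period from the subject's Randomization date – 10 weeks" up to the Week 52 visit. Earlier records therefore enter the calculation.
- *Exclusion of an earlier recurring record:* "If the concomitant medication record end date + gap factor < Randomization date, the duration of the record is 0".
- *Credited days otherwise:* "Start date will be the latest of (concomitant medication record start date, randomization date, treatment start date"; and "Stop date will be the earliest of (concomitant medication record stop date + gap factor, first transfusion date (RBC or whole blood", with further caps at treatment stop plus one day and Week 52.
- *Baseline, recurring frequency:* "Stop date will be the earliest of (concomitant medication record stop date + gap factor and the day before randomization".
- *One time dose:* no gap factor applies. The rule giving zero on-treatment credit opens "If concomitant medication record start date < treatment start date, or if earliest of (first transfusion date". At baseline, such a dose in the 10 weeks before randomization gets frequency 1 and 7 days, so it counts in full.

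**The concern.** If a recurring record's last dose was given before randomization, but its stop date plus gap reaches randomization, the days from then on are credited to the outcome. The baseline rule stops at the day before randomization, so the same days are missing from the covariate. No section reconciles this with the three definitions above. The one-time-dose rule applies the opposite principle to an infusion on the same date.

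Randomized treatment cannot influence iron given before it began. This endpoint carries the only superiority test in the hierarchy (Protocol 9.4.3, one-sided 2.5% after the primary gate). Baseline IV iron is in the ANCOVA to absorb pre-existing differences in iron use. Moving part of it into the outcome weakens that adjustment and misstates on-treatment use. The supportive analysis in 8.1.1.2 ignores treatment stop and transfusion but states no different gap rule, so it does not clearly remove the carry-in.

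**Working it through.** **The plan's gap factors.** The formula gap = 7/frequency − 1 gives 2.5, 1.33, 0.75 and 0.4 days for 2, 3, 4 and 5 times weekly. It gives 0 for once daily, 6 for weekly, 13 for every 2 weeks, 27 for every 4 weeks and 29.4 for monthly (the SAP states 29). BID, TID and every 12 hours are set to 0. The rule therefore spreads each dose forward over its own dosing interval. A single-day record keeps its full dose (0.986 of it for monthly).

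**Inputs.** Frequencies and gaps come from the 10.6.3.2 tables. The dose sizes and dates are assumptions, and results scale linearly with dose. Treatment is assumed to start on the randomization date (counted as 0 below, so Day −1 is the day before), with no transfusion.

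**One 500 mg infusion, Day −1, coded once a month**

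- On treatment: credited from 0 to −1 + 29 = 28, which is 29 days. 500 × 0.23 × 29/7 = 476.4 mg.
- Baseline: 1 day. 500 × 0.23 × 1/7 = 16.4 mg.

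**The same infusion under other codes and dates (baseline mg / on-treatment mg)**

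| Code | Day −1 | Day −7 | Day −14 | Day −28 |
|---|---|---|---|---|
| One time dose | 500 / 0 | 500 / 0 | 500 / 0 | 500 / 0 |
| Once daily | 500 / 0 | 500 / 0 | 500 / 0 | 500 / 0 |
| Once a week | 71 / 429 | 500 / 0 | 500 / 0 | 500 / 0 |
| Every 2 weeks | 36 / 464 | 250 / 250 | 500 / 0 | 500 / 0 |
| Every 4 weeks | 18 / 482 | 125 / 375 | 250 / 250 | 500 / 0 |
| Once a month | 16 / 476 | 115 / 378 | 230 / 263 | 460 / 33 |

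**Courses whose code fits the dosing**

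- Weekly 100 mg × 5, Day −29 to Day −1, one record: on treatment 0 to −1 + 6 = 5, which is 6 days, 100 × 1 × 6/7 = 85.7 mg; baseline 29 days, 100 × 29/7 = 414.3 mg. As five one-time records: 0 and 500 mg.
- Three times weekly 100 mg ending Day −1: on treatment 1.33 days, 100 × 3 × 1.33/7 = 57 mg.

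**Conversion to mg/month.** The denominator over 52 weeks is 365/30.4375 = 11.99 months; for a subject stopping at 12 weeks it is 85/30.4375 = 2.79 months.

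- Weekly course: 85.7/11.99 = about 7 mg/month.
- Three times weekly: 57/11.99 = about 5 mg/month.
- Monthly-coded 500 mg: 476.4/11.99 = 39.7 mg/month over 52 weeks; 476.4/2.79 = about 171 mg/month at 12 weeks.

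**A record running throughout.** Weekly 100 mg from Day −29 to beyond Week 52: the rule gives 100 × 365/7 = 5214 mg. Counting by administration date gives 52 × 100 = 5200 mg.

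**The case against.** The strongest defence is that the gap factor is deliberate smoothing. SAP 10.6.3.2 says it wants a continuous dose, and spreading each dose over its interval does that. For a record running through the whole period, carry-in at the start and truncation at the end nearly cancel (5214 against 5200 mg). That stands, and it confines the defect to records that end before randomization, where nothing offsets the carry-in.

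Several stronger readings are tempting, but the documents do not support them.

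- *Pre-randomization iron is removed from baseline.* It is split: days before randomization stay in the covariate. The split also requires the record to end within its gap of randomization, and cannot occur for daily or more frequent codes.
- *Shifts of 400 mg or more are typical.* They need a single large infusion coded as weekly or less often, although the eCRF offers a one-time code. Nothing indicates how often sites would do this.
- *Screening repletion makes late pre-randomization iron common.* Screening may be extended for IV iron, but footnote 1 to Protocol Table 6 requires ferritin and TSAT to be re-assessed after supplementation and before randomization. That makes eligibility iron on the last day or two unlikely.
- *The comparison is biased.* The milligrams carried in come from before randomization, so they are balanced in expectation. Dividing by time on treatment could unbalance mg/month only if that time differed by arm, and the documents give no figure for this.
- *Truncation at the end is a separate error favouring an arm.* A 500 mg every-4-weeks dose given 5 days before Week 52 does count as 500 × 0.25 × 6/7 = 107 mg. But that is the counterpart of the same smoothing, and no difference between arms is shown.

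It is also fair that dose-by-dose attribution would need administration dates. The derivation uses only record start, stop and frequency.

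**Conclusion.** The defect is real and narrow. A recurring record that ends before randomization, but within its gap factor, has part of its dose counted in the outcome and lost from the covariate, contrary to three SAP definitions and to the one-time-dose rule. Under the assumed doses, the carry-in is about 5 to 7 mg/month per affected subject for ordinary weekly or three-times-weekly courses ending on Day −1. It is about 40 mg/month for a 500 mg infusion coded monthly, and several times that when treatment time is short. The consequences are added noise, weaker covariate adjustment and distorted reported mg/month. The effect on power and type I error is not quantified, because the number of affected records is unknown. It should be corrected before unblinding because the change is small and the endpoint is the only gated superiority test.

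**What to change.** Amend SAP 10.6.3.2 as follows.

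1. **Randomization to Week 52:** set a recurring record's duration to 0 when its own stop date, without the gap factor, is before treatment start.
2. **Baseline:** when the record's own stop date is before randomization, credit its duration through stop date plus gap, without cutting at the day before randomization. The existing 10-week start limit stays.
3. **Week 28-52 and quarterly windows:** apply the same own-stop-date principle at the start of each window. For adjoining quarters, keep the full duration in the quarter where the record ended, so that iron does not drop out of both.
4. **Leave the smoothing unchanged** for records that span treatment start or the end cutoff. Carry-in and truncation largely offset there, and exact attribution would need administration dates.

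Check on the examples: the weekly course becomes 100 × 35/7 = 500 mg at baseline and 0 on treatment. The Day −1 monthly-coded infusion becomes 500 × 0.23 × 30/7 = 492.9 mg and 0; the shortfall from 500 is the rounding of the monthly frequency and gap.

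The cost is a few lines of SAP text and derivation code before unblinding. It uses only record dates already in the derivation, so no new data are needed.

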10.6.3.3. Time to Rescue

Time to Stopping Randomized Treatment Due to Meeting Rescue Criteria
Meeting Rescue Evaluation Criteria and Rescue Criteria

 Subjects meeting evaluation criteria for rescue are identified from the Rescue Treatment eCRF. Subjects with a record on this form are considered to have met evaluation criteria for rescue. It is possible that a subject could be evaluated for rescue more than once, and in that case a subject would have multiple records on this form. Subjects unable to be evaluated for rescue are subjects who met evaluation criteria for rescue, but were unable to be assessed at the 4 week check (e.g., subjects who died, permanently discontinued randomized treatment or withdrew from the study before the 4 week check). The outcome of initial intervention eCRF field on the Rescue Treatment eCRF will be blank for these subjects. Subjects meeting rescue are identified by the response 'Met rescue criteria' to the outcome of initial intervention question on the Rescue Treatment eCRF.
Event Date

 Treatment stop date when the primary reason and subreason for randomized treatment stop are: 
 Primary reason: Subject reached protocol-defined stopping criteria Subreason: Rescue
General Definitions

 Time to event (days) = date of event – randomization date +1 Censored time (days) = censoring date – randomization date + 1 Rescue person years = (cumulative total time to stopping randomized treatment for subjects who stopped randomized treatment due to meeting rescue criteria + cumulative total of censoring time for subjects who did not stop randomized treatment due to meeting rescue criteria) / 365.25 Rescue incidence rate (per 100 person years) = (100 * number of subjects who stopped randomized treatment due to meeting rescue criteria) / rescue person years Rescue absolute rate difference (per 100 person years) = daprodustat rescue incidence rate (per 100 person years) – darbepoetin alfa rescue incidence rate (per 100 person years)

CONFIDENTIAL

201410

Time to Stopping Randomized Treatment Due to Meeting Rescue Criteria
Time Period for Treatment Discontinuation

The period for treatment discontinuation begins at randomization. The end of this time period is defined as follows:
 
 • For subjects who did not take randomized treatment, use the date of randomization • For subjects whose treatment stop date is missing and who took randomized treatment, use study conclusion date • For subjects either continuing on study past treatment stop date or completing/withdrawing on the same day as treatment stop date, use treatment stop date 
Any events that occurred before the start of this time period are considered to be prior to the time period for treatment discontinuation, and any endpoints that occurred after the end of this time period are considered to be post the time period for treatment discontinuation.

10.6.3.4. RBC and Whole Blood Transfusion Endpoints

Number of RBC and Whole Blood Transfusions	

 • The number of transfusions associated with each RBC and Whole Blood Transfusion record is determined by the frequency, start date, end date and number of units, as described below. • Only on-treatment transfusions are included. “End date” below refers to the end date defined for the transfusion, or the end of the on-treatment period, if sooner (see Section 10.4.1). • For records with a frequency of “Once only” or “Continuous infusion”, each record is considered to be a single transfusion (regardless of start and end dates or number of units). • For records with a frequency of “Once daily”, the number of transfusions will equal the duration (end date – start date +1). • For records with a frequency of “PRN”, or where the frequency is unknown, the number of transfusions for each record will be equal to the number of units recorded. • For other transfusion records, the number of transfusions will equal the duration (end date – start date +1) times a multiplier, as defined below: The number of transfusions should be rounded up to the nearest integer. 	
Frequency	Multiplier
QM	0.033
Every 2 weeks	0.071
Once a week	0.14
Q4D	0.25
2 times per week	0.29
Q3D	0.33
3 times per week	0.43
Every other day	0.5
4 times per week	0.57
5 times per week	0.71
BID	2
Q12H	2

CONFIDENTIAL

201410

TID	3
Q8H	3
QID	4
Q6H	4
5 times per day	5
Q4H	6

Number of RBC and Whole Blood Transfusion Events

- RBC and Whole Blood Transfusion Events are defined by grouping together on-treatment transfusion records.
- Transfusion records are grouped into the same Transfusion Event if the transfusion start/end dates match with or are contained within an Admission/Discharge period, (based on the Hospitalization page in the eCRF).
- For example, the following transfusion records would be grouped into a single Transfusion Event, because each transfusion is contained within the same hospital admission/discharge period:

Dose	Frequency	Transfusion Dates		Hospitalisation		Comment
		Start Date	End Date	Admission	Discharge	
1 unit	Once only	16FEB2019	16FEB2019	15FEB2019	26FEB2019	1 Transfusion Event
1 unit	Once only	19FEB2019	19FEB2019	15FEB2019	26FEB2019	

- Transfusion records not matching with an Admission/Discharge period are considered to be the same Transfusion Event if the gap between transfusions is 5 days or less, with further details provided below. For any subject where the frequency is PRN and the transfusion start date \neq end date, the dates of individual transfusions are unknown and the number of transfusion events will be counted as one.
- In the case of a sequence of more than two transfusions, transfusions are considered to be the same Transfusion Event if the gap between each transfusion and the start date of the first transfusion in the sequence (the “anchor” transfusion) is 5 days or less. The first transfusion that is greater than 5 days after the “anchor” transfusion is not included in the Transfusion Event, and it becomes the new “anchor” transfusion for a new Transfusion Event.
- In the example below, transfusion records 1 and 2 would be grouped into a single Transfusion Event, because the gap between the transfusions (17JAN2019 to 18JAN2019) was 5 days or less. Record 3 falls outside this Transfusion Event because the gap between the start date (22JAN2019) and the previous anchor date (16JAN2019) is more than 5 days. Therefore, 22JAN2019 becomes the new “anchor” transfusion used to define the next Transfusion Event. This pattern is repeated, if necessary. N.B. “anchor” transfusions are shown in bold.

#	Dose	Frequency	Transfusion Dates		Comment
			Start Date	End Date	
1	1 unit	Once only	16JAN2019	16JAN2019	1 Transfusion Event
2	1 unit	Once only	19JAN2019	19JAN2019	
3	1 unit	Once only	22JAN2019	22JAN2019	1 Transfusion Event

CONFIDENTIAL

201410

4	1 unit	Once only	25JAN2019	25JAN2019	
5	1 unit	Once only	28JAN2019	28JAN2019	1 Transfusion Event

- Where a non-integer number of units has been entered on the eCRF, this will be rounded up to the nearest integer prior to any subsequent derivation (if necessary).

Number of Units

- The number of RBC and whole blood units are derived from blood transfusion records. The number of units associated with each record is determined by the frequency, start date, end date and dose (i.e. number of units recorded), as described below:
- Only units associated with on-treatment transfusions are included. “End date” below refers to the end date defined for the transfusion, or the end of the on-treatment period, if sooner (see section 10.4.1).
- For records with the frequency recorded as “Once only” or “Continuous infusion”, the total number of units associated with each record is the number of units recorded (regardless of start and end dates)
- For records with the frequency recorded as “Once daily”, the total number of units associated with each record will equal the number of units recorded multiplied by the duration (end date – start date +1)
- For records with the frequency recorded as “PRN”, the total number of units will be equal to the number of units recorded (regardless of start and end dates)
- For other records, the number of units will be equal to the number of units recorded multiplied by the duration (end date – start date +1) times a multiplier, as defined for Number of RBC and Whole Blood Transfusions above
- The table below provides multipliers for converting various reported units to Units (which should be rounded to up nearest integer). For example, a transfusion of 450ml represents a single unit:
(450 x 0.0025) = 1.125 (rounded up to 2 Units)

Reported Units	Multiplier
Units	1
Milliliters (ml or CC)	0.0025
Milligram (mg)	0.0025
Milligrams/millilitres (mg/ml)	0.0025

- Where a non-integer number of units has been entered on the eCRF, this will be rounded up to the nearest integer prior to any subsequent derivation (if necessary).
- Where a transfusion record has been entered with a missing number of units, the number of units associated with the record will be assumed to be 1 unit.

Evaluation Period (Weeks 28 to 52)

- Only transfusion events with a start date from date of week 28 visit to the date of the week 52 visit will be included
- Patient Years (PY) = (cumulative total time from date of week 28 visit to the date of the week 52 visit, for subjects who did not withdraw from randomized treatment during the evaluation period + cumulative time from date of week 28 visit to the date of withdrawal from randomized treatment, for subjects who withdrew from randomized treatment during the evaluation period) / 365.25

CONFIDENTIAL

201410


 • Transfusion Events per 100 PY = (100 * number of on-treatment RBC or whole blood transfusion events during the evaluation period) / Patient Years (PY) • Transfusions per 100 PY = (100 * number of on-treatment RBC or whole blood transfusions during the evaluation period) / Patient Years (PY) • Units per 100 PY = (100 * number of on-treatment RBC or whole blood transfusion units during the evaluation period) / Patient Years (PY)
Randomization to Week 52

 • Only transfusion events with a start date from the date of randomization to the date of the week 52 visit will be included • Patient Years (PY) = (cumulative total time from date of randomization to the date of the week 52 visit, for subjects who did not withdraw from randomized treatment prior to week 52 + cumulative time from date of randomization to the date of withdrawal from randomized treatment, for subjects who withdrew from randomized treatment prior to week 52) / 365.25 • Transfusion Events per 100 PY = (100 * number of on-treatment RBC or whole blood transfusion events from the date of randomization to the date of the week 52 visit) / Patient Years (PY) • Transfusions per 100 PY = (100 * number of on-treatment RBC or whole blood transfusions from the date of randomization to the date of the week 52 visit) / Patient Years (PY) • Units per 100 PY = (100 * number of on-treatment RBC or whole blood transfusion units from the date of randomization to the date of the week 52 visit) / Patient Years (PY)
Time to First On-Treatment RBC or Whole Blood Transfusion

 • Event Date = Start date for the first on-treatment RBC or whole blood transfusion received after treatment start date • Censoring Date = date of stopping randomized treatment for subjects who stopped randomized treatment, or date of study completion for subjects who did not stop randomized treatment • Time to event (days) = date of event – treatment start date + 1 • Censored time (days) = censoring date – treatment start date + 1

 • Person years (PY) = (cumulative total time to event date, for subjects who received at least one on-treatment RBC or whole blood transfusion + cumulative total of censoring time for subjects who did not receive at least one on-treatment RBC or whole blood transfusion) / 365.25 • Incidence rate per 100 PY = (100 * number of subjects who received at least one on-treatment RBC or whole blood transfusion) / person years • Absolute rate difference (per 100 person years) = daprodustat incidence rate (per 100 person years) – darbepoetin alfa incidence rate (per 100 person years)
Time Period for On-Treatment Transfusions

 • The period for capturing on-treatment transfusions begins on the treatment start date + 1 day. The end of this time period is defined as follows: 
 ○ For subjects continuing on study past the (treatment stop date + 1 day), use (treatment stop date + 1 day) ○ For subjects whose study withdrawal/completion date is on or before (treatment stop date + 1 day), use date of study withdrawal/completion

Model Specification

 Analysis of time to first RBC or whole blood transfusion will be performed using an analysis model identical to that described for the time to stopping randomized treatment due to meeting rescue criteria (Section 8.1.2). Analysis will include only transfusion occurring during the on-treatment period..
Model Results Presentation

 The model results presentation will be identical to the co-primary MACE model results, with the following exception: A single one-sided p-value for the test of superiority of daprodustat vs. darbepoetin alfa will be presented (i.e. there will be no test for non-inferiority). A Kaplan-Meier plot will be produced showing the survival function for time to first RBC or whole blood transfusion.

